
Primary Endpoint(s): MTD as defined by the occurrence of dose-limiting toxicity (DLT) among 2 dose schedules
Secondary Endpoint(s): Overall response rate (ORR), with a target if at least 15% to be continued for a phase 2 study.
Exploratory Endpoint(s):

Median response duration for responders, median time of progression to AML, median overall survival (OS) and 1- and 2-year OS rates.Assessment of the dynamic quantitative change in proportion of MDSCs and PD-1 expression in BM with combined therapy and correlation with any observed clinical responses.
Study Design: This will be a phase 1b study [see schema]. The proposed dosing of ENT has been

previously tested in MDS as single agent and shown to be well-tolerated. While the combination of ENT with the anti-PD1, pembrolizumab (MK-3475) has not been studied clinically in MDS patients, based on mechanisms of action it is unlikely that this combination would have overlapping toxicities.

PART 1: ENT has been previously evaluated as a single agent therapy in patients with MDS at these doses and has been well tolerated. The ENT monotherapy run-in part (cycle 1) will allow to study the changes in MDSCs at pre- and post- ENT treatment (the end of cycle 1) to dissect the effects of ENT monotherapy from those of the combined ENT/anti-PD1 therapy.

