Assessment of response will occur after 4 combination cycles and similar to part 1, those who achieve an objective response or SD will continue to receive the therapy till progression. Patients who progress or respond and subsequently lose response will be withdrawn from study. BM biopsy/aspirate and PB samples will be done at baseline, after first cycle of ENT monotherapy, every 2 cycles of combined therapy, and at time of progression or study discontinuation. Formal safety assessment will be performed at end of DLT-observing period (i.e. 1 ENT monotherapy cycle and 2 cycles of combined therapy) for each patient) for each DL to assess for any unexpected autoimmune or other toxicity. The cycle duration will be 21 days, the maximum number of treatment cycles of entinostat will be 18 cycles and for pembrolizumab (MK-3475) the maximum number of cycles will be 17. Cycle 2 to cycle 18, will have concurrent administration.

The following early stopping rule for excess toxicity in the expansion cohort will be used: We will cease enrollment in the expansion phase at the dose determined from dose escalation part of the study if we observe two or more DLTs among the first six evaluable patients enrolled in the expansion cohort. An evaluable patient is any patient who received a study drug. If the true toxicity rate is 50% or greater at the MTD then this rule will stop the trial with probability at least .89. Similarly, if the true toxicity rate is 33% at the MTD then this stopping rule will end the trial with probability .65. In that event, a new expansion cohort will start at the dose level immediately below the dose level that was expanded. If the dose level being expanded is dose level -1, then the study will be terminated.

Study Schema

Study design

Dose Escalation Schedule		
Dose Level	Dose*	
	Entinostat	Pembrolizumab
Level -1(Backup dose level)	8mg po D1	200mg
Level 1 (starting dose level)	8mg po D1,8	200mg
Level 2	8mg po D1,8,15	200mg

Number of Patients: 6-27

Main Criteria for Inclusion/Exclusion:

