Definition of DLT: DLT will be defined as the occurrence of any of the following during the first 2 cycles of combined therapy unless the event can clearly be determined to be unrelated to the study drugs.

- Any grade 3 or 4 non-hematologic toxicity with the following exceptions: A) Transient laboratory abnormalities that can be treated or resolve to grade 2 or less within 72 hours.
- Grade 4 hematologic toxicity, including treatment-associated aplasia lasting >42 days from the last dose of study drug. Given that severe anemia, neutropenia and thrombocytopenia are features of advanced MDS and commonly encountered in this patient population, they will not be used to define DLT except if associated with prolonged treatment-associated aplasia as described above.
- Patients with grade 3 immune related adverse events will be removed from the treatment and this will be considered to be a DLT as well as any other immune-related adverse event that results in pembrolizumab interruption, dose modification, or discontinuation of therapy.
-
- Definition of secondary outcomes/endpoints: Overall response rate (ORR: The sum of rates of complete response [CR], partial response [PR], and hematologic improvement [HI]) as defined by the modified IWG-2006 criteria (**Appendix A**) with a goal of at least 20% to be considered clinically meaningful for further evaluation in larger studies.
- Analytic plan for primary objective: Toxicities will be tabulated and graded according to the Common Terminology Criteria for Adverse Events Version 5 (CTCAE-5). DLT will be assessed after the first 2 cycles of combined therapy.

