- Analytic plan for secondary objectives/ Sample size justification: Currently there is no therapy that has been shown to prolong survival in MDS in the post-DNMTi setting and that the expected best response in patients receiving supportive care only in post-DNMTi setting is negligible (1% or less). It is generally accepted that a $\geq 15\%$ ORR in the post-DNMTi is clinically meaningful and would be worth further evaluation in larger studies. We therefore calculated that treating a total of 21 patients in the combination arm (6 in the first part of the study and 15 in the second part of the study) to test the difference of ORR between 1% (null hypothesis-supportive care only) and 15% (alternative hypothesis, combination therapy). The null hypothesis response rate of 1% will be rejected if we observe 2 or more favorable responses. This criterion has significance level between .02 and .03 using a one-sided binomial test. The criterion has power between .84 and .93 for testing an alternative response rate of 15%.
- The total number of patients enrolled in the study will range from 6 to 27.
- Analytic plan for exploratory objectives: The quantitative change in MDSCs (% MDSCs by

flow cytometry, QIF score by AQUA) during treatment with the ENT/anti-PD1 combined therapy will be estimated using mixed effects models to take into account the within-patient correlation. Likelihood ratio tests will be performed to confirm if random intercepts and slopes are necessary in the model. The fixed effect for change in MDSCs over time will be evaluated for significance. The variability in the rate of change in MDSCs across patients will also be examined. The association between the clinical outcome and a meaningful reduction in MDSCs, which will be defined after a review of the data, will be assessed with the chi-square test. The quantity of MDSCs at baseline and during treatment as continuous variables can also be compared between responding and non-responding patients using a t-test or Mann-Whitney U-Test, if more appropriate.

TABLE OF CONTENTS

SCHEMA	2
TABLE OF CONTENTS	10
1. OBJECTIVES	13
1.1 Primary Objectives.....	13
1.2 Secondary Objectives.....	13
1.3 Exploratory objectives	13
2. BACKGROUND	13
2.1 Myelodysplastic syndrome (MDS)	13
2.2 CTEP IND Agents.....	16
2.3 Rationale for combining anti-PD1 antibody with entinostat in MDS after DNMTi failure	21
2.4 Correlative Studies Background (full correlative proposal attached in Appendix J).....	21

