5.3 Dose Expansion Cohorts

Once the RP2D is reached, an additional 15 patients will be treated at this dose. For the expansion cohort, patients will continue to be monitored for occurrence of DLT. Participants who go off-study during the 1st cycle of entinostat will be replaced in the escalation phase. Participants who do not complete the first 2 cycles of combined therapy without experiencing a DLT (as DLT period is defined in the first 2 combined therapy cycles) will also be replaced. To be DLT-evaluable, the patient must complete the first two cycles of combined therapy without experiencing a DLT. Any patient who is dose reduced during the entinostat run-in first cycle due to entinostat-related toxicity will be analyzed on the dose level that corresponds to the reduced dose level delivered during the first cycle of combined therapy.

The following early stopping rule for excess toxicity in the expansion cohort will be used: We will cease enrollment in the expansion phase at the dose determined from dose escalation part of the study if we observe two or more DLTs among the first six evaluable patients enrolled in the expansion cohort. An evaluable patient is any patient who received a study drug. If the true toxicity rate is 50% or greater at the MTD then this rule will stop the trial with probability at least .89. Similarly, if the true toxicity rate is 33% at the MTD then this stopping rule will end the trial with probability .65. In that event, a new expansion cohort will start at the dose level immediately below the dose level that was expanded. If the dose level being expanded is dose level -1, then the study will be terminated.

Monitoring of all safety and toxicity data is done by the Principal Investigator and the Corresponding Organization on a real-time basis as data are entered into Medidata Rave using the Web Reporting Module. All participating sites are expected to notify the Principal Investigator when a DLT has occurred.

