Assessment of response will occur after 4 combination cycles and similar to part 1, those who achieve an objective response or SD will continue to receive the therapy till progression. Patients who progress or respond and subsequently lose response will be withdrawn from study. BM biopsy/aspirate and PB samples will be done at baseline, after first cycle of ENT monotherapy, every 2 cycles of combined therapy, and at time of progression or study discontinuation. Formal safety assessment will be performed after the first 6 patients are enrolled and each have received at least 5 cycles (i.e. 1 ENT monotherapy cycle and 4 cycles of combined therapy (DL1, DL2) for each patient) to assess for any unexpected autoimmune or other toxicity.

Primary Endpoint(s): MTD will be defined by the occurrence of DLT among 2 dose schedules (see section 5.2)

Definitions of DLT: see section 5.2

The following early stopping rule for excess toxicity in the expansion cohort will be used: We will cease enrollment in the expansion phase at the dose determined from dose escalation part of the study if we observe two or more DLTs among the first six evaluable patients enrolled in the expansion cohort. An evaluable patient is any patient who received a study drug. If the true toxicity rate is 50% or greater at the MTD then this rule will stop the trial with probability at least .89. Similarly, if the true toxicity rate is 33% at the MTD then this stopping rule will end the trial with probability .65. In that event, a new expansion cohort will

start at the dose level immediately below the dose level that was expanded. If the dose level being expanded is dose level -1, then the study will be terminated.

Secondary Endpoint(s): Overall response rate (CR, PR, and HI) as defined by the modified International working group 2006 (IWG-2006) criteria for CR, PR, HI ([Appendix A1](#) and [Appendix A2](#)) with at least 15% to be continued

Exploratory Endpoint(s):

- Median response duration for responders, median time of progression to AML, median overall survival (OS) and 1- and 2-year OS rate
- Assessment of the dynamic quantitative change in proportion of MDSCs in BM with combined therapy (target of reducing to <10%) and correlation with any observed clinical responses

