13.2 Sample Size/Accrual Rate

We expect to accrue 1-2 patients with MDS per month once the study is open.

Currently there is no therapy that has been shown to prolong survival in MDS in the post-DNMTi setting and that the expected best response in patients receiving supportive care only in post-DNMTi setting is negligible (1% or less). It is generally accepted that a $\geq 15\%$ ORR in the post-DNMTi is clinically meaningful and would be worth further evaluation in larger studies.

The total number of patients enrolled in the study will range from 21 to 27. The null hypothesis response rate of 1% (only supportive care) will be rejected if we observe 2 or more favorable responses. These criterion has significance level between .02 and .03 using a one-sided binomial test. This criterion has power between .84 and .93 for testing an alternative response rate of 15% with the combination therapy. Therefore, we will treat a total of 21 patients in the combination arm (6 in the first part of the study and 15 in the second part of the study).

DOMESTIC PLANNED ENROLLMENT REPORT						
Racial Categories	Ethnic Categories				Total	
	Not Hispanic or Latino		Hispanic or Latino			
	Female	Male	Female	Male		
American Indian/ Alaska Native	1	1	1	1	4	
Asian	1	1	0	0	2	
Native Hawaiian or Other Pacific Islander	1	0	0	0	1	
Black or African American	1	1	1	1	4	
White	4	4	1	1	10	
More Than One Race	0	0	0	0		
Total	8	7	3	3	21	

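### The response rate worth pursuing is 20% in one place and 15% elsewhere, and total enrolment is given both as 6-27 and as 21-27, with a maximum that the written rules do not guarantee

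*Combined protocol and SAP*

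**What the plan says.** **ORR target.** The synopsis, under Statistical Methods (definition of secondary outcomes), sets the ORR "with a goal of at least 20% to be considered clinically meaningful for further evaluation in larger studies". The synopsis list of endpoints gives the ORR "with a target if at least 15% to be continued for a phase 2 study". Section 13.1 repeats "with at least 15% to be continued". The sample-size text in the synopsis and Section 13.2 both call an ORR of 15% or more clinically meaningful and worth larger studies. They test 1% against 15% and reject 1% on 2 or more responses, with one-sided significance level .02 to .03. On power the synopsis says: "The criterion has power between .84 and .93 for testing an alternative response rate of 15" (per cent).

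**Enrolment.** The synopsis header has "Number of Patients: 6-27" and its statistical text says "The total number of patients enrolled in the study will range from 6 to 27". Section 13.2 says "The total number of patients enrolled in the study will range from 21 to 27". Both sample-size texts also give 21 as the number treated for the ORR test: 6 from part 1 and 15 from part 2.

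**Rules that determine enrolment.** Escalation allows at most 6 evaluable patients per dose level. Two or more DLTs at DL-1 terminate the study (synopsis, Sections 5.1 and 13.1). Two or more DLTs among the first six expansion patients stop that expansion, and then "a new expansion cohort will start at the dose level immediately below the dose level that was expanded" (Section 5.3; also the synopsis, Section 12.1 and Section 13.1). No passage gives the size of that new cohort. The synopsis and Section 5.3 also provide for replacing patients.

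**The concern.** The 20% and the 15% describe the same decision, whether the combination deserves further study, in adjacent parts of one synopsis section. They cannot be reconciled as a goal and a minimum. If the percentages are applied to the observed rate, the same count of responders could be reported as meeting or as missing the target.

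The two enrolment ranges are given in the same sentence with different lower limits, and both claim to cover everyone enrolled. The upper limit matters for accrual planning and oversight: a team that follows the re-expansion rule as written may pass 27 without breaking any other instruction, depending on how it sizes the new cohort.

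**Working it through.** **1. Reproduce the stated test.** Inputs from the synopsis sample-size text and Section 13.2: null rate .01, alternative .15, reject at 2 or more responses, N = 21 to 27.

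P(X ≥ 2) = 1 − (1−p)^N − N·p·(1−p)^(N−1)

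At N = 21, p = .15: 1 − .0329 − .1221 = .845. At N = 27, p = .15: 1 − .0124 − .0592 = .928.

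| N | p = .01 | p = .15 | p = .20 |
|---|---|---|---|
| 21 | .0185 | .845 | .942 |
| 27 | .0297 | .928 | .981 |

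The plan's .02-.03 and .84-.93 are confirmed. They belong to 15%; no stated design figure rests on 20%.

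**2. Counts on which the two targets disagree** (15% ≤ k/N < 20%, read as observed rates).

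| N | k | probability if true ORR is 15% / 20% |
|---|---|---|
| 21 | 4 | .191 / .216 |
| 22 | 4 | .199 / .211 |
| 23 | 4 | .204 / .204 |
| 24 | 4 | .209 / .196 |
| 25 | 4 | .211 / .187 |
| 26 | 4, 5 | .377 / .371 |
| 27 | 5 | .172 / .191 |

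Examples: 4/21 = 19.0%, 5/27 = 18.5%. The rejection boundary itself, 2/21 = 9.5% (exact 95% CI 1.2% to 30.4%), lies below both targets.

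**3. Lower limit.** The shortest completed trial is 3+3+15 = 21. Termination at DL-1 can end the study earlier: 3 at DL1 plus 6 at DL-1 is 9, and 6 requires DL-1 to stop after 3. So 21 is not a minimum for patients enrolled.

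**4. Upper limit.** 27 = 6 (DL1) + 6 (DL2) + 15. With each stopped expansion halted at 6 patients:

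- New cohort a full 15: one stop gives 6+6+6+15 = 33; two stops give 6+6+6+6+15 = 39.
- New cohort only completing the planned 15: one stop gives 12+6+9 = 27; two stops give 12+6+6+3 = 27.
- A fresh 9 each time (21 expansion patients in all after two stops): 27 after one stop, 12+6+6+9 = 33 after two.

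One route passes 27 without any expansion being stopped. The Section 5.2 table adds 3 patients at the next lower level when a level fails and only 3 were treated below it. Then DL1 3, DL2 6 (fails), DL1 3 more (fails), DL-1 6, expansion 15 gives 33. The narrative in the synopsis, Section 5.1 and Section 13.1 instead sends a failed DL2 straight to expansion at DL1, so the route does not exist there.

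**5. How often.** Exact enumeration of these rules. Assumptions not in the documents: DLT rates at DL-1/DL1/DL2 of 1/6 flat, .20 flat, 1/3 flat, .10/.17/.25 and .10/.20/.33; 6 patients at DL-1; no replacements and no safety-committee changes. Ranges cover the five rate profiles, and either 3 or 6 patients at DL2 after 0/3.

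| New cohort | P(N > 27), narrative text | P(N > 27), Section 5.2 refill |
|---|---|---|
| full 15 | .092-.257 | .105-.313 |
| fresh 9 each time | .015-.051 | .020-.078 |
| completes the planned 15 | 0 | .005-.027 |

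P(N < 21) is 5-17% in four profiles and 53% at a flat 1/3.

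**The case against.** The best defence is that the sponsor's 27 is right on a natural reading. If a restarted expansion only fills up the planned 15, two stops still end at 27, and under the narrative escalation text nothing exceeds it before replacements. That stands: a reader might infer that 27 is simply wrong, and the documents do not support this. What they support is that 27 holds on one unstated reading and fails on others.

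Second, a reader might infer that the error rate is inflated, since 2 or more responses would have a significance level of .043 at N = 33 and .058 at N = 39. Those figures require every enrolled patient to be pooled across up to three dose levels. The sample-size texts build the test on 6+15 patients, and Section 13.4 reports response rates by cohort. Section 13.5.2 puts eligible patients in the main response analysis without saying how a restarted expansion is handled. The point is therefore open, and inflation is not a stated consequence of the plan.

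Third, the 20% is a single outlier on a secondary endpoint of a phase 1b trial, and the formal rule uses neither 15% nor 20%. This is correct and limits the weight, but it does not remove the contradiction. Fourth, 21-27 in Section 13.2 sits beside the alpha and power it belongs to, and 6-27 allows for early termination. That explains both ranges, yet each is labelled as total enrolment.

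**Conclusion.** The point holds as three reconciliations and should be fixed.

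- **ORR target:** 20% in one passage conflicts with 15% in the other statements of the target. Only 15% matches the stated power. Read as observed rates, the conflict affects one count at each N from 21 to 27 (two at N = 26), with probability about .17 to .22 (about .37 to .38 at N = 26) when the true ORR is 15% or 20%. The test of 1% is unaffected, and its stated alpha and power are correct for 21 to 27 patients.
- **Lower limit:** 6 and 21 cannot both be the minimum enrolled, and 21 is not one. This needs no assumption.
- **Upper limit:** 27 is not guaranteed. It can become 33 or 39 if a new expansion cohort is a full 15 (27 passed in about 9-31% of trials). It stays 27 if the new cohort completes the planned 15, apart from the Section 5.2 refill route (about 0.5-2.7%). Replacements add to any of these totals. The percentages rest on assumed DLT rates; the totals do not.

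**What to change.** 1. Use 15% in every passage and delete the 20% goal in the synopsis. State whether the 15% in the endpoint lists (synopsis and Section 13.1) is a true rate the trial is powered to detect or an observed cut-off for continuing. Add that 2 or more responses rejects only a 1% rate (2/21 = 9.5%, exact 95% CI 1.2% to 30.4%).
2. Replace 6-27 and 21-27 with one enrolment range or cap that covers early termination, re-expansion and replacements. Keep 21-27 only as the N range for which alpha and power are given, and label it so.
3. State the size of a new expansion cohort.
4. Reconcile the Section 5.2 table with the narrative in the synopsis, Section 5.1 and Section 13.1 on what follows a failed DL2. Which rule applies is the sponsor's decision.
5. State which patients enter the ORR test after a restarted expansion. Only if all enrolled patients are pooled, give alpha and power at the larger N: .043/.968 at 33, .058/.986 at 39.

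The cost is wording in a few passages, at most one extra line of alpha and power, and either a higher stated maximum or an explicit cap.

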1. OBJECTIVES

1.1 Primary Objectives

To assess safety, tolerability, and identify the maximum tolerated dose (MTD) of entinostat given in combination with pembrolizumab (MK-3475).

1.2 Secondary Objectives

To obtain a preliminary estimate of efficacy of entinostat in combination with pembrolizumab (MK-3475).

1.3 Exploratory objectives

To assess the dynamic quantitative change in measurable immunological biomarkers (proportions of myeloid-derived suppressor cells [MDSCs], and programmed death protein-1 [PD-1] expression in bone marrow) with the combined epigenetic-immunotherapy and correlation with any observed clinical responses.

2. BACKGROUND

2.1 Myelodysplastic syndrome (MDS)

Novel treatment options after azacitidine failure represent a major unmet clinical need in MDS

Myelodysplastic syndromes (MDS) are among the most common hematologic malignancies and constitute the most common chronic myeloid malignancy in USA^{16,17}. The age-adjusted incidence in USA has been estimated at 3.3-4.6 per 100,000 persons (exceeding that of acute myeloid leukemia [AML]) which translates into more 20,000 cases per year^{16,17} with some estimates putting the number at 45,000 new cases in the year 2003¹⁸. Patients with MDS have widely variable prognosis with expected survival that ranges from few months to many years reflecting the complex pathophysiology of the disease¹⁹. Approximately one third of MDS patients have higher-risk (HR)-disease, typically defined with International Prognostic Scoring System (IPSS) of intermediate-2 or high risk groups [\[Appendix B\]](#), and have an expected median survival of less than one year if treated only with supportive measures²⁰. The only curative treatment modality for HR-MDS is allogeneic bone marrow transplantation (allo-SCT), but due to the typically advanced age and multiple comorbidities that characterize these patients, less than 5% of patients undergo allo-SCT²¹. Aside of allo-SCT, the DNA methyltransferase inhibitor (DNMTi) azacitidine is the only treatment proven to prolong survival in HR-MDS¹. Nonetheless, the survival advantage with azacitidine has a median duration of only 9.5 months (24.5 vs 15 months in median overall survival [OS])¹. Additionally, only 50% of patients receiving azacitidine exhibit an objective response (complete response rate [CR] only 17%) with most patients eventually relapsing within 2 years¹.

Failure of DNMTi therapy is associated with dismal prognosis with a survival of less than 6 months². To date and despite extensive research, no drug or combination of drugs have improved

survival of MDS patients in the post-DNMTi failure setting in randomized trials, and there is currently no standard of care. Therefore, improving outcomes of MDS patients with failure of DNMTi remains a top clinical priority ³. For those patients with DNMTi failure who are not candidates or do not want to undergo allo-SCT, clinical trials or best supportive therapy are considered reasonable treatment approaches as intensive chemotherapy is associated with significant toxicity and low response rates, and is usually only used in a minority of patients as a bridge to allo-SCT for eligible patients who are willing to undergo the procedure and have a graft source. As the mechanisms of primary and secondary resistance to DNMTi therapy are poorly understood, it has been difficult to rationally design targeted therapies that are effective to salvage patients after DNMTi therapy failure occurs.

Histone deacetylase inhibitors (HDACi) demonstrated modest activity in MDS

Histone deacetylase inhibitors (HDACi) comprise a group of drugs that share the ability to inhibit the important epigenetic eraser enzymes histone deacetylases (HDAC) but vary significantly in terms of their structure, target specificity, and pharmacokinetic profiles. There are 18 different HDACs in human that belong to 4 different classes, and the HDACi vary significantly in their class and enzyme specificity. In addition, HDACi have different pharmacokinetic profiles with significant difference in their half-lives, administration modes and metabolism. As single agents, multiple HDACi have been well tolerated in MDS but exhibited only a modest clinical activity ^{4,5}. Therefore, interest to develop these agents further has focused on combination-based strategies, usually with HMAs. To date, no HDACi-HMA combination has improved survival of MDS patients in randomized studies when used in the frontline or post-HMA failure setting. Several studies of HDACi are ongoing in the post-HMA failure setting, usually by adding the HDACi to azacitidine with the primary goal of achieving (in case of primary resistance) or re-acquiring (in case of secondary resistance) a clinical response.

One of the HDACs studied in MDS is entinostat: an orally bioavailable, isotype-selective class 1-specific HDACi with long half-life (100 hours). A phase I clinical trial published in abstract form at Johns Hopkins University combined entinostat with a lower dose, prolonged administration schedules of azacitidine²². In this trial, patients were treated with SQ azacitidine for 10 days at different dose levels (30, 40, or 50mg/m²/day) and given oral entinostat (2, 4, 6, 8 mg/m²/dose) on days 3 and 10. Out of 31 enrolled patients, 13 had MDS, 4 had chronic myelomonocytic leukemia (CMML), and 14 had acute myeloid leukemia (AML). Patients were evaluable for response if they received 4 or more cycles of treatment. Of the 27 evaluable patients, 12 had responses (2 CR, 4 had partial responses [PR], and 6 bilineage hematologic improvement [HI]) according to the International Working Group [IWG] 2000 criteria. The 50mg/m²/day dose of azacitidine D1-10 and the entinostat 4 mg/m²/dose on D3 and D10 were subsequently studied in the randomized phase 2 ECOG1905 study versus azacitidine monotherapy at the same 50mg/m²/day dose D1-D10²³. Both arms achieved rates of trilineage hematologic normalization (32% for azacitidine monotherapy and 27% for combination) that were exceeded that of the historical control in which the standard regimen of azacitidine at 75mg/m²/day D1-7 was used (16% in CALBG9221 trial). While there was no survival advantage with the combination compared to azacitidine, this could be potentially related to pharmacologic antagonism caused by early administration of entinostat, a potent cell-cycle inhibitor with a long half-life of 4.5 days, in each cycle (day 3) which could have inhibited incorporation of azacitidine into DNA and subsequent cell cycling²³. These findings suggest that while entinostat has a modest activity in MDS, HMAs might not be the best choice

for combination-based regimen with entinostat. Exploration of alternative agents to combine with entinostat in the post-DNMTi failure setting might be a more rational approach.

Rationale for use of immune-check point inhibitors in MDS after DNMTi failure

Programmed death receptor-1 (PD-1) is a molecule expressed on antigen-stimulated T-cells and induces downstream signaling that cause inhibition of T-cell proliferation, cytokine release, and cytotoxicity²⁴. Recent data showed that multiple types of tumor are capable of evading the immune system by expressing PD-1 ligands (e.g. PD-L1) which engages the PD-1 receptor on the surface of cytotoxic T-cell leading to suppression of their activity⁶. Immune checkpoint blockade with anti-PD-1 and anti-PDL-1 antibodies (and anti-cytotoxic T-Lymphocyte-associated antigen 4 [CTLA-4] antibodies) has emerged as a novel promising approach to reverse this phenomenon and has resulted in a significant and durable clinical activity in some patients with advanced solid malignancies especially metastatic melanoma⁹. Pembrolizumab (MK-3475, KEYTRUDA®) is a humanized monoclonal IgG4-kappa antibody that inhibits PD-1 with highly selectivity which has recently been granted an accelerated approval in 2014 by the FDA for treatment of refractory metastatic melanoma (Keytruda product information. http://www.merck.com/product/usa/pi_circulars/k/keytruda/keytrudapi.pdf). In a large open-label, multicenter phase 1b trial, 173 adult patients with refractory metastatic melanoma were randomized to IV pembrolizumab at 2 or 10 mg/kg every 3 weeks⁹. With a median follow-up of 8 months, the ORR was 21-26% at both doses. Survival data has not yet been reported. Most common drug-related adverse events of any grade in the 2 and 10 mg/kg doses were fatigue (33% vs 37%), pruritus (26% vs 19%), and rash (18% vs 18%). Grade 3 fatigue (in 3%) was the only drug-related grade 3 to 4 adverse event reported in more than one patient⁹, suggesting that the drug is well tolerated and is potentially associated with less severe side effects than the CTLA-4 inhibitor ipilimumab. Advanced non-small cell lung cancer showed 19.4% of ORR and 12.5 months of median duration of response²⁵. Metastatic or refractory squamous cell carcinoma of the head and neck showed 18% of ORR to pembrolizumab in a phase Ib trial²⁶. Pembrolizumab is now approved for advanced melanoma, non-small cell lung cancer, and advanced head and neck cancer.

Several lines of evidence suggest that the immune system dysregulation is important in the pathogenesis and progression of MDS and that targeting key immune effector and regulatory steps can be a novel therapeutic approach for disease control in MDS²⁷. We are in fact evaluating the use of the CTLA-4 inhibitor ipilimumab in a multi-center CTEP-sponsored phase 1 study in DNMTi-refractory MDS and there are other active phase 1 studies of anti-PD1 and anti-PD-L1 antibodies in MDS.

Data suggests that during disease progression in MDS the clonal blasts become more aggressive while the non-clonal immune cells become less efficient via unknown mechanisms¹². In a Chinese study of 38 MDS patients, the percentages of CTLA-4, PD-1 and CD25 were significantly higher in patients with MDS compared to normal and the differences of CTLA-4, PD-1 and the ratio of CTLA-4/CD28 between patients with HR-MDS and lower-risk (LR)-MDS were more significant with progression of MDS further suggesting involvement of the PD-1 axis in MDS progression²⁸. Using MDS cell lines and patient samples, Kondo and colleagues¹² showed that the expression of an immune-inhibitory molecule PD-L1 (B7-H1, CD274) was induced by interferon-γ (IFN-γ) and tumor necrosis factor-α (TNF-α) on MDS blasts and that these blasts exhibited more potent intrinsic proliferative capacity than PD-L1-negative MDS blasts. Additionally, these PD-L1-

positive blasts suppressed T-cell proliferation and induced T-cell apoptosis in allogeneic co-cultures. In BM samples, blasts from HR-MDS patients expressed PD-L1 molecules more often compared with those from LR-MDS patients while the BM T-cells over-expressed PD-1 molecules¹². These findings suggest that PD-L1-positive MDS blasts have an intrinsic proliferative advantage and induce T-cell suppression through interactions with PD-1 receptors leading potentially to disease progression and suggesting a role for therapeutic intervention¹². The MD Anderson group studied mRNA in CD34+ cells from 124 patients with MDS, AML and chronic myelomonocytic leukemia (CMML) and found that 34%, 15%, and 8% had aberrant up- regulation (≥ 2 -fold) in PD-L1, PD-1 and CTLA4, respectively¹³. PD-L1 protein expression was observed in MDS CD34+ cells, whereas stromal and non-blast cellular elements were positive for PD-1. More importantly, in subgroup of patients treated with DNMTi therapy, PD-L1, PD-1 and CTLA4 expression was increased with the patients who exhibited resistance to DNMTi therapy showing higher relative up-regulation in gene expression than responding patients. Furthermore, treatment of leukemia cells with decitabine resulted in a dose-dependent up- regulation of these genes and partial hypomethylation of PD-1 in leukemia cell lines and human samples¹³. In addition to providing further evidence to the role of PD-1/PD-L1 axis in MDS progression, these results suggest this axis might mediate resistance to DNMTi therapy and provide rationale for combining epigenetic therapy with immune checkpoint blockade using an anti-PD1 antibody as a novel therapeutic approach to improve outcomes of HR-MDS patients.

